### **2.3 PARTICIPANT REGISTRATION AND STATUS UPDATE PROCEDURES**

Registration and status updates (e.g. when a participant is taken off protocol therapy and when a participant is taken off-study) will take place per CCR SOP ADCR-2, CCR Participant Registration & Status Updates found [here](#).

#### **2.3.1 Treatment Assignment Procedures**

##### **Cohorts**

Patients will be assigned to the appropriate cohort depending on prior checkpoint inhibitor therapy and documented or reviewed radiologic responses to prior checkpoint inhibitor therapy. Whenever possible prior scans will be loaded to our PACS and reviewed for cohort 2A and 2B.

Subjects from all cohorts will be treated with a flat dose of M7824 (1200 mg) every 2 weeks (+/- 3 days for scheduling issues).

Number	Name	Description
1	Cohort 1A	Checkpoint inhibitor naïve patients who are cisplatin-ineligible
2	Cohort 1B	Checkpoint inhibitor naïve patients who are refractory post-platinum therapy
3	Cohort 2A	Checkpoint inhibitor refractory patients with prior Complete Response (CR) or Partial Response (PR) as per RECIST 1.1 as best response
4	Cohort 2B	Checkpoint inhibitor refractory patients with Stable Disease (SD) or Progressive Disease (PD) as per RECIST 1.1 as best response

### Arms

Number	Name	Description
1	Arm 1	Treatment with fixed dose of M7824 (1200 mg) every 2 weeks

### Arm assignment

Subjects from all cohorts (1A, 1B, 2A and 2B) will be directly assigned to Arm 1.

## 2.4 BASELINE EVALUATION

Tests done at screening do not need to be repeated on baseline (C1D1) if performed within 21 days prior to initiation of study therapy except physical exam, ECOG, vital signs, blood tests (CBC with differential, acute care, mineral and hepatic panels, amylase, lipase, LDH, GGT, thyroid function tests) and pregnancy test (repeated if >7 days). Please refer to Section 2.2 for details.

Correlative Studies: Please refer to Section 5.2 for information regarding collection of blood, and tissue for correlative research studies.

[figure not shown]
## 3 STUDY IMPLEMENTATION

### 3.1 STUDY DESIGN

- This is an open label, non-randomized, single arm phase II trial of M7824 in checkpoint inhibitor naïve and refractory patients with urothelial carcinoma.
- We will plan to use a fixed dose of 1200 mg delivered IV every 2 weeks (Q2W) based on the recent NCI-led phase I dose-escalation trial of M7824 in advanced solid tumors (NCT02517398) [33]. M7824 appeared to have a manageable safety profile and early evidence of clinically efficacy. The MTD was not reached in this study at 20mg/kg and

- PD-L1 receptor occupancy and sequestration of TGF- $\beta$  isoforms 1-3 was achieved at M7284 dose levels >1mg/kg.
- A maximum of 68 evaluable subjects will be enrolled in checkpoint naïve [Cohort 1] and checkpoint inhibitor refractory [Cohort 2] patients with urothelial carcinoma of the bladder.
    - Cohort 1A: Checkpoint inhibitor naïve patients who are cisplatin-ineligible
    - Cohort 1B: Checkpoint inhibitor naïve patients who are refractory post-platinum therapy
    - Cohort 2A: Checkpoint inhibitor refractory patients with Complete Response (CR) or Partial Response (PR) as per RECIST 1.1
    - Cohort 2B: Checkpoint inhibitor refractory patients with Stable Disease (SD) or Progressive Disease (PD) as per RECIST 1.1
  - Enrollment of 2-3 patients per month is expected on this trial; thus, 2 to 3 years is anticipated as the accrual period.
  - Restaging will be performed every 2 cycles (8 weeks). Safety/tolerability analysis and secondary clinical efficacy analysis will be ongoing through cycle 4. Patients can continue study drug in all arms provided there is no confirmed evidence of progression, unacceptable toxicity or withdrawal from the study.

### 3.1.1 Schema

1L - First line; 2L - Second line; CR - complete response; PR - partial response; SD - stable disease; PD - progressive disease

### Treatment Schema of M7824: 28-day cycle (D1/D15)

If appropriate screening imaging is done within 21 days of C1D1 repeat screening imaging is not required.

Cycles and Day	C1D1	C1D15	C2D1	C2D15	C3D1	C3D15	C4D1	C4D15
M7824 (1200mg IV Q2W)	X	X	X	X	X	X	X	X

## 3.2 DRUG ADMINISTRATION

### 3.2.1 M7824

See Section 14.1 for drug preparation, administration and infusion times.

## 3.3 DOSE MODIFICATIONS

### 3.3.1 M7824

M7824 is planned to be administered at 1200 mg (flat dose) every two weeks. Dosing may be delayed up to 12 weeks for toxicity or logistical reasons, including the inability of the patient to get to the clinic. Dose reductions are not allowed.

#### 3.3.1.1 Premedications

Current experience revealed that infusion-related reactions (IRRs) to bintrafusp alfa occur seldomly and are generally mild to moderate in severity. Therefore, administration of a premedication is generally not required.

If an Investigator deems necessary to administer a premedication to a particular participant, an antihistamine (e.g. 25 to 50 mg diphenhydramine) and paracetamol (acetaminophen, 500 to 650 mg intravenously or equivalent oral dose) 30 to 60 minutes prior to bintrafusp alfa infusion is recommended. Premedication should be administered for subsequent bintrafusp alfa doses based upon clinical judgment and presence/severity of prior infusion reactions. This regimen may be modified based on local treatment standards and guidelines as appropriate, provided it does not include systemic corticosteroids. If Grade  $\geq 2$  infusion reactions are seen during the first two infusions, premedication should not be stopped. Steroids as premedication are not permitted.

#### 3.3.1.2 Adverse Drug Reactions (ADRs) Requiring Treatment Discontinuation

**Any Grade 4 ADRs require permanent treatment discontinuation** except for single laboratory values out of normal range that do not have any clinical correlate, and resolve to Grade  $\leq 1$  or baseline grade within 7 days with adequate medical management. Grade 3 or 4 symptomatic endocrinopathies (e.g., thyroiditis or hypophysitis), treatment should be delayed and treatment started according to NCCN guidelines. If condition improves to Grade 1, treatment may be resumed.

Subjects with grade 4 amylase or lipase abnormalities must permanently discontinue treatment. If the participant develops any evidence of pancreatitis, it should be managed accordingly.

**Any Grade 3 ADRs require treatment discontinuation except for any of the following:**

- Transient ( $\leq 6$  hours) Grade 3 flu-like symptoms or fever, which is controlled with medical management.
- Transient ( $\leq 24$  hours) Grade 3 fatigue, local reactions, headache, nausea, emesis that resolves to  $\leq$  Grade 1 or Baseline grade.
- Tumor flare phenomenon defined as local pain, irritation, or rash localized at sites of known or suspected tumor that resolves within 7 days with optimal medical management.
- Any single Grade  $\geq 3$  drug-related transaminase, alkaline phosphatase, or bilirubin abnormality with no other associated laboratory (or other) abnormality that is not associated with symptoms or clinical manifestations of hepatitis. If the liver function abnormality not associated with symptoms or clinical manifestations of hepatitis has not resolved to Grade  $\leq 1$  within the subsequent 2 cycles (28 days), the subject should permanently discontinue treatment with M7824.
- Subjects with asymptomatic Grade 3 drug-related amylase or lipase abnormalities may continue treatment.
- .
- Grade 3 Hgb decrease ( $< 8.0$  g/dL) that is clinically manageable with blood transfusions or erythroid growth factor use.
- Increases in Eastern Cooperative Oncology Group performance status (ECOG PS)  $\geq 3$  that resolves to  $\leq 2$  by Day 1 of the next cycle (infusions should not be given if the ECOG PS is  $\geq 3$  on the day of M7824 administration and should be delayed until ECOG PS  $\leq 2$ ).
- Keratoacanthoma and squamous cell carcinoma of the skin. Any suspicious skin lesion should be biopsied for confirmation of diagnosis and be surgically removed as indicated by dermatologist and a dermatological consult obtained.
- Other immune-related ADRs, see NCCN guidelines for the management of immune related adverse events

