**Design:**

- This is an open label, non-randomized, single arm phase II trial of M7824 in checkpoint inhibitor naïve and previously treated patients with urothelial carcinoma of the bladder.
- M7824 (intravenous 1200 mg fixed dose) will be delivered every 2 weeks
- Patients will receive treatment in cycles consisting of 4 weeks.
- A maximum of 75 subjects will be enrolled in this trial.

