## 3.3.1.3 Adverse Drug Reactions Requiring Management

**Any Grade 2 ADR should be managed as follows:**

- If a Grade 2 ADR resolves to Grade  $\leq 1$  by the last day of the current cycle, treatment may continue.
- If a Grade 2 ADR does not resolve to Grade  $\leq 1$  by the last day of the current cycle but it is manageable and / or not clinically relevant, it is possible the infusion will be given on the following cycle.

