## 16 APPENDICES

### 16.1 APPENDIX A: STUDY CALENDAR

	Screening 	All Cycles (28 days each)												EOT visit	Follow up 	
		C1 D1	C1 D15	C2 D1	C2 D15	C3 D1	C3 D15	C4 D1	C4 D15	C5 D1	C5 D15	C6 D1	C6 D15 & Beyond			
History/PE incl weight and skin assessment 	X	X	X	X	X	X	X	X	X	X	X	X	X	X	X	
Confirmation of pathology/Biopsy 	X					X									X	
ECOG, Vital Signs	X	X	X	X	X	X	X	X	X	X	X	X	X	X	X	
Tumor evaluation/measurements	X					X				X			X 			
M7824 		X	X	X	X	X	X	X	X	X	X	X	X	X		
Lab assessments 	X	X	X	X	X	X	X	X	X	X	X	X	X	X	X	X
Pregnancy test 	X	X		X		X		X		X		X				
Lymphocyte phenotyping 	X															
ECG	X															
CT C/A/P or CT C+MRI A/P 	X					X				X			X 	X		
Follow-up Phone calls/emails																X 
Correlative Studies	Please refer to Section 5.2															

*Abbreviated Title: Phase II M7824 in UC*  
*Version Date: 06/23/2021*

1. Pre-treatment tissue biopsy and/or tissue availability is mandatory. On-treatment biopsy is required unless obtaining biopsy is not technically or clinically feasible. Post-treatment biopsy is optional.
2. Tests done at screening do not need to be repeated on baseline (C1D1) if performed within 21 days prior to initiation of study therapy.
3. M7824 will be delivered intravenously every 2 weeks (+/- 3 days).
4. Vital signs must be measured within 30 minutes before and 30 minutes following M7824 infusions. In addition, at least one time during the infusion of M7824.
5. Laboratory assessments: CBC with differential, acute care panel (sodium, potassium, chloride, total CO2 (Bicarbonate), creatinine, glucose, urea nitrogen), mineral panel (albumin, calcium total, magnesium total, phosphorus), hepatic panel (alkaline phosphatase, ALT/GPT, AST/GOT, total bilirubin, direct bilirubin), ionized calcium, amylase, lipase, TSH with reflex T3 and T4, LDH, total protein, GGT, PT/INR, PTT, and urine analysis. Hepatitis B and C will be done at screening only.
6. For females of childbearing-potential (within 3 days prior to initiation of study therapy).
7. Lymphocyte phenotyping tests will be done to check the eligibility of HIV positive patients. HIV-positive patients are eligible only if CD4 counts are greater than 350 cells/mm^3 and viral load is undetectable.

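### The stopping limit for an isolated Grade 3 or higher liver abnormality equates 2 cycles with 28 days, but 2 cycles are 56 days in this protocol, and the rule conflicts with the 7-day limit for Grade 4 laboratory values

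*Combined protocol and SAP*

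**What the plan says.** Section 3.3.1.2 lists the exceptions to the rule that a Grade 3 adverse drug reaction ends treatment. One exception covers any single Grade 3 or higher "drug-related transaminase, alkaline phosphatase, or bilirubin abnormality with no other associated laboratory (or other) abnormality", provided there are no symptoms or clinical manifestations of hepatitis. Its time limit is resolution to Grade 1 or less; failing that "within the subsequent 2 cycles (28 days), the subject should permanently discontinue treatment with M7824".

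The cycle length is stated consistently elsewhere. The précis (Design) says "Patients will receive treatment in cycles consisting of 4 weeks". The treatment schema in Section 3.1.1 shows a 28-day cycle with doses on days 1 and 15. The sample schedule in Section 5.2 and the study calendar in Appendix A (16.1) also use 28 days. Section 3.1 makes its own conversion: "Restaging will be performed every 2 cycles (8 weeks".

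The Grade 4 paragraph of Section 3.3.1.2 requires permanent discontinuation for any Grade 4 reaction. It exempts a single laboratory value without clinical correlate if that value resolves to Grade 1 or less "or baseline grade within 7 days with adequate medical management".

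**The concern.** The liver bullet is a mandatory stopping rule for a drug whose important identified risks include immune-related hepatitis (Table 2). It gives its limit in two units that disagree under the protocol's own definition of a cycle. Two investigators with the same unresolved Grade 3 value could both follow the text and stop treatment four weeks apart. The error can run either way: exposure beyond the intended limit, or premature and permanent loss of therapy in a patient with metastatic disease.

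The second problem is scope. The bullet appears as an exception to the Grade 3 rule, yet its wording takes in Grade 4, which has its own rule and its own, much shorter, laboratory exception. The text does not say which governs an isolated Grade 4 liver value.

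**Working it through.** **Inputs**
- Stated limit: 2 cycles, equated with 28 days (Section 3.3.1.2, Grade 3 exceptions).
- Cycle length: 28 days (précis; Sections 3.1.1 and 5.2; Appendix A).
- Dosing interval: 14 days (précis; Section 2.3.1).
- The protocol's own conversion: 2 cycles = 8 weeks (Section 3.1).
- Grade 4 isolated-laboratory limit: 7 days (Section 3.3.1.2, Grade 4 paragraph).

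**Step 1: try to reproduce the stated equivalence.** Days = cycles × days per cycle = 2 × 28 = 56, not 28. As a check, 56 / 7 = 8 weeks, which agrees with Section 3.1. The stated figure is not reproduced.

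**Step 2: find what would reproduce it.** The implied cycle length is 28 / 2 = 14 days, which is the dosing interval. So 28 days is one protocol cycle (28 / 28 = 1) or two dosing intervals (28 / 14 = 2). The protocol nowhere defines a 14-day cycle. Wording carried over from a plan with 14-day cycles would explain the slip, but that is an inference.

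**Step 3: size of the ambiguity for Grade 3.** 56 − 28 = 28 days, and 56 / 28 = 2. In dosing intervals, the window is 28 / 14 = 2 or 56 / 14 = 4. The bullet does not say that dosing is held during the window. Appendix A schedules laboratory tests at every dosing visit, so either limit can be applied in practice. The dose-delay allowance in Section 3.3.1 is up to 12 weeks (12 × 7 = 84 days), longer than both readings, so it does not decide between them.

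**Step 4: Grade 4 overlap.** Consider an isolated Grade 4 liver value without symptoms that returns to Grade 1 or less on a given day:

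| Day of resolution | Grade 4 rule (7 days) | Liver bullet, 28-day reading | Liver bullet, 56-day reading |
|---|---|---|---|
| 1 to 7 | may continue | may continue | may continue |
| 8 to 28 | stop permanently | may continue | may continue |
| 29 to 56 | stop permanently | stop permanently | may continue |
| after 56 | stop permanently | stop permanently | stop permanently |

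The gap is 28 − 7 = 21 days on the 28-day reading and 56 − 7 = 49 days on the 56-day reading. From day 8 to day 28 the rules conflict whichever meaning of a cycle is used.

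**Step 5: does another rule settle it?** Table 2 sets bilirubin limits for hepatitis, and Appendix C (Table A2, hepatitis) requires permanent discontinuation at Grades 3 and 4. Both address hepatitis, whereas the bullet covers abnormalities without its manifestations. Neither says which window applies here.

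**The case against.** The strongest reply is that 28 is printed in the bullet, and reaching 56 means setting that number aside and recalculating from a definition elsewhere. Nearby text supports 28. Section 3.3.1.3, on unresolved Grade 2 reactions, says "it is possible the infusion will be given on the following cycle", and Section 3.3.1.12 links the next treatment to the second cycle after the event; both seem to use the word for a dosing interval. This makes 28 days the more likely intention and is a good reason to adopt it as the default. It does not remove the defect. The count of 2 cycles is equally explicit, the second meaning is never defined, and this usage would mean that the safety rules employ one term in two senses.

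On Grade 4, it can be said that an exception listed under a Grade 3 heading does not displace the separate Grade 4 rule, and that Section 3.3.1.8 also points to stopping at Grade 4 for immune-related events. That is a sensible reading by heading. However, the neighbouring haemoglobin and amylase/lipase bullets are limited to Grade 3, while the liver bullet expressly goes higher. That could be deliberate or a slip, and the text does not show which. The 49-day gap requires both less natural readings at once and is a worst case only.

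The weekly team meeting and the principal investigator's review of each patient's adverse events (Section 7.4.1) make divergent application less likely, but they do not supply the missing rule. The hepatitis rules narrow the group affected; the documents give no frequency for such events.

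**Conclusion.** The concern holds on both parts. The limit contradicts itself: 28 against 56 days, a difference of 28 days or a factor of two. The Grade 4 overlap is a true conflict from day 8 onward, with a gap of 21 days on the 28-day reading and, at worst, 49 on the 56-day reading.

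The unit mismatch rests only on the protocol's stated cycle length. The Grade 4 conflict rests on taking the bullet's grade range as written. Which limit the sponsor intended cannot be determined from the documents, and nothing here shows that 56 days is the right one. This is a drafting inconsistency in a safety rule. It should be corrected, and it has no bearing on sample size, alpha, power or the response analysis.

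**What to change.** Reword the one bullet in Section 3.3.1.2:
- Give the window in days only and remove the count of cycles. Use 28 days (one cycle, two dosing intervals) unless the sponsor's clinical team confirms that 56 is intended.
- Limit the bullet to Grade 3, so that isolated Grade 4 liver values follow the 7-day rule. If the sponsor intends a longer window for Grade 4 liver values, the Grade 4 paragraph should say so and name the exception. That is a clinical decision for the sponsor.

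Visits, laboratory schedule, sample size and analysis are unchanged. The cost is the rewording and the IRB approval that the Statement of Compliance requires before any amendment takes effect; it can be included with the next amendment.

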## 3.3.1.3 Adverse Drug Reactions Requiring Management

**Any Grade 2 ADR should be managed as follows:**

- If a Grade 2 ADR resolves to Grade  $\leq 1$  by the last day of the current cycle, treatment may continue.
- If a Grade 2 ADR does not resolve to Grade  $\leq 1$  by the last day of the current cycle but it is manageable and / or not clinically relevant, it is possible the infusion will be given on the following cycle.

## 3.3.1.4 Infusion-related Reactions (IRR)

Signs and symptoms usually develop during or shortly after drug infusion and generally resolve completely within 24 hours of completion of infusion. These possible IRR are identified based on a list of MedDRA PTs and divided into reactions versus signs and symptoms.

- An IRR should be considered when onset is on the day of infusion (during or after the infusion) or the day after the infusion (irrespective of resolution date) for any infusion related reaction, drug hypersensitivity, anaphylactic reaction, hypersensitivity and/or Type 1 hypersensitivity.
- Signs and symptoms of infusion related reactions and hypersensitivity/allergic reactions should be considered when onset is on the day of infusion (during or after the infusion) and resolved completely with the end date within 2 days after onset. Signs and symptoms may include but not limited to: fever, chills or shaking, rigors, flushing, hypotension, wheezing, pruritus, rash and hypoxemia, shortness of breath, back or neck pain, facial swelling, dizziness, feeling of passing out.
- Infusion-related reactions and hypersensitivity reactions (Grades 1 to 4) should be handled according to the Guidelines provided in [Table 1](#).
- Management of immune-mediated reactions is described in [Table 2](#).

**Table 1:** Treatment Modifications for Symptoms of Infusion-related Reactions including Immediate Hypersensitivity

NCI-CTCAE Grade	Treatment Modification

Grade 1 - mild Mild transient reaction; in general, infusion interruption not indicated; intervention not indicated
	
 
• Increase monitoring of vital signs as medically indicated as participants are deemed medically stable by the attending Investigator.
 
• Hold infusion if deemed necessary by the investigator.
 


Grade 2 – moderate Therapy or infusion interruption indicated but responds promptly to symptomatic treatment (for example, antihistamines, nonsteroidal anti-inflammatory drugs, narcotics, IV fluids); prophylactic medications indicated for ≤ 24 h.
	
 
• Stop the infusion of the study intervention.
 
• Increase monitoring of vital signs as medically indicated as participants are deemed medically stable by the attending Investigator.
 
• If symptoms resolve quickly, resume infusion at 50% of original rate with close monitoring of any worsening signs and symptoms, otherwise dosing held until resolution of symptoms with mandated premedication for the next scheduled visit.
 
• If not improving, consider administration of glucocorticoids and stop the infusion for that day.
 
• If the participant has a second IRR Grade ≥ 2 on the slower infusion rate despite premedication, the infusion should be stopped, and the investigator may consider withdrawal of this participant from the study.
 

Grade 3 or Grade 4 – severe or life-threatening
 
 
○ Grade 3: Prolonged (for example, not rapidly responsive to symptomatic
 
	
 
• Stop the infusion of study intervention immediately and disconnect infusion tubing from the participant with additional appropriate medical measures and closely monitor until
 

medication and/or brief interruption of infusion); recurrence of symptoms following initial improvement; hospitalization indicated for clinical sequelae.
 
 
○ Grade 4: Life-threatening consequences; urgent intervention indicated.
 
	
deemed medically stable by the attending Investigator. Hospitalization and/or close monitoring is recommended
 
Administration of glucocorticoids may be required
 
 
• For Grade 3 or 4 IRRs, permanent discontinuation of study intervention is mandated.
 

Once the infusion is interrupted or rate reduced to 50% of previous infusion rate, it must remain decreased for all subsequent infusions.
 
For all types and grades of infusion reactions, details about drug physical constitution, method of preparation, and infusion must be recorded.
 
Participants should be instructed to report any delayed reaction immediately.
	

1 IRR=infusion-related reactions, IV=intravenous, NCI-CTCAE=National Cancer Institute-Common Terminology Criteria for Adverse Event, NSAIDs=nonsteroidal anti-inflammatory drugs.
	

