### 3.3.1.5 Additional Modifications for Subjects with Grade 2 Infusion-related Reactions

If, in the event of a Grade 2 infusion-related reaction that does not improve or worsens after implementation of the modifications indicated in [Table 1](#).

- Management of immune-mediated reactions is described in [Table 2](#).

**Table 1:** Treatment Modifications for Symptoms of Infusion-related Reactions including Immediate Hypersensitivity

NCI-CTCAE Grade	Treatment Modification

Grade 1 - mild Mild transient reaction; in general, infusion interruption not indicated; intervention not indicated
	
 
• Increase monitoring of vital signs as medically indicated as participants are deemed medically stable by the attending Investigator.
 
• Hold infusion if deemed necessary by the investigator.
 

Grade 2 – moderate Therapy or infusion interruption indicated but responds promptly to symptomatic treatment (for example, antihistamines, nonsteroidal
	
 
• Stop the infusion of the study intervention.
 
• Increase monitoring of vital signs as medically indicated as participants are deemed medically stable by the attending Investigator.
 

anti-inflammatory drugs, narcotics, IV fluids); prophylactic medications indicated for $\leq 24$ h.	
 
• If symptoms resolve quickly, resume infusion at 50% of original rate with close monitoring of any worsening signs and symptoms, otherwise dosing held until resolution of symptoms with mandated premedication for the next scheduled visit.
 
• If not improving, consider administration of glucocorticoids and stop the infusion for that day.
 
• If the participant has a second IRR Grade <math>\geq 2</math> on the slower infusion rate despite premedication, the infusion should be stopped, and the investigator may consider withdrawal of this participant from the study.
 

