
Grade 3 or Grade 4 – severe or life-threatening
 
 
○ Grade 3: Prolonged (for example, not rapidly responsive to symptomatic medication and/or brief interruption of infusion); recurrence of symptoms following initial improvement; hospitalization indicated for clinical sequelae.
 
○ Grade 4: Life-threatening consequences; urgent intervention indicated.
 
	
 
• Stop the infusion of study intervention immediately and disconnect infusion tubing from the participant with additional appropriate medical measures and closely monitor until deemed medically stable by the attending Investigator. Hospitalization and/or close monitoring is recommended Administration of glucocorticoids may be required
 
• For Grade 3 or 4 IRRs, permanent discontinuation of study intervention is mandated.
 

Once the infusion is interrupted or rate reduced to 50% of previous infusion rate, it must remain decreased for all subsequent infusions. For all types and grades of infusion reactions, details about drug physical constitution, method of preparation, and infusion must be recorded. Participants should be instructed to report any delayed reaction immediately.
	

2 IRR=infusion-related reactions, IV=intravenous, NCI-CTCAE=National Cancer Institute-Common Terminology Criteria for Adverse Event, NSAIDs=nonsteroidal anti-inflammatory drugs.
	

(including reducing the infusion rate by 50%), the investigator may consider treatment with corticosteroids and the infusion of M7824 should be stopped for that day. At the next infusion, the investigator may consider the addition of H2-blocker antihistamines (for example, famotidine), in addition to premedication, for select subjects. However, prophylactic steroids are NOT permitted. If the subject has a second infusion-related reaction Grade  $\geq 2$  on the slower infusion rate, with or without the addition of further medication to premedication, the infusion should be stopped and the subject may be removed from M7824 treatment at the discretion of the investigator.

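### Section 3.3.1.5 leaves removal from M7824 to the investigator after a second infusion reaction of Grade 2 or above, which contradicts Table 1's mandatory stop when that reaction is Grade 3 or 4

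*Combined protocol and SAP*

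**What the plan says.** Section 3.3.1.4 refers IRRs of all grades to one table: "Infusion-related reactions and hypersensitivity reactions (Grades 1 to 4) should be handled according to the Guidelines provided in" Table 1. The Grade 3 and 4 row of that table ends with "For Grade 3 or 4 IRRs, permanent discontinuation of study intervention is mandated". It makes no exception for whether the reaction is the patient's first or a later one.

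Section 3.3.1.5 gives extra steps for a Grade 2 reaction that has not improved, or has worsened, after the Table 1 measures. Its last sentence begins "If the subject has a second infusion-related reaction Grade" and sets the threshold at 2 or above, on the slower rate, with or without added premedication. It then directs that "the infusion should be stopped and the subject may be removed from M7824 treatment at the discretion of the investigator".

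The Grade 2 row of Table 1 has a similar clause for a second reaction, again triggered at Grade 2 or above: "on the slower infusion rate despite premedication, the infusion should be stopped, and the investigator may consider withdrawal of this participant from the study". Table 1 is printed twice, once in Section 3.3.1.4 and once in the middle of Section 3.3.1.5.

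The general rules for adverse drug reactions (ADRs) in Section 3.3.1.2 say "Any Grade 4 ADRs require permanent treatment discontinuation", apart from certain isolated laboratory values, with separate handling of endocrinopathies. For Grade 3 they say "Any Grade 3 ADRs require treatment discontinuation except for any of the following", followed by a list.

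**The concern.** A stopping rule for a severe infusion reaction should give one answer. Read literally, the last sentence of Section 3.3.1.5 gives the investigator a choice that Table 1 withholds. Because it is the more specific text on second reactions, a reader could take it as the governing rule and treat re-dosing as allowed.

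What is at stake is re-exposure of a patient who has just had a severe or life-threatening reaction on an already slowed infusion. There is also a smaller administrative consequence. If dosing did continue, it would be unclear whether that was protocol non-adherence to be logged under Section 8.8 or a permitted use of discretion.

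**Working it through.** The plan states no figure on this point and no arithmetic applies. The check is a comparison of the rules by grade and by action.

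**Which grades each rule covers.**
- Last sentence of Section 3.3.1.5, second reaction on the slower rate: Grade 2 and above, so Grades 2, 3 and 4 among reactions where further dosing is a question.
- Table 1, Grade 3 and 4 row: Grades 3 and 4, whether first or later.
- Overlap: Grades 3 and 4. A second reaction of exactly Grade 2 falls only under the discretionary rule, and there is no conflict.

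**What each rule requires within the overlap.**
- Table 1, Grade 3 and 4 row: stopping the study drug for good is mandatory.
- Section 3.3.1.5: ending the current infusion is directed, but taking the patient off M7824 is optional.
- Both concern the same act, continued treatment with M7824. One makes it compulsory to end treatment and the other does not, so this is a contradiction in the wording.

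**Whether the same holds for the Grade 2 row of Table 1.** The grade overlap is identical, but the optional act is different: withdrawal from the study. Section 3.6.1 lists the reasons for coming off protocol therapy and says that patients off treatment can stay on study for follow-up, including survival. Section 3.6.2 lists the off-study criteria separately. After a second Grade 3 reaction, the drug can be stopped as mandated while study withdrawal remains a matter for consideration. Both rows can be obeyed together, so as printed they do not contradict each other.

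**Whether another rule settles precedence.** No sentence in Sections 3.3.1.4 or 3.3.1.5 does so expressly. Three things favour the mandate:
1. Section 3.3.1.4 routes IRRs of Grades 1 to 4 to Table 1, where a Grade 3 or 4 reaction falls in the mandatory row.
2. The general Grade 4 rule in Section 3.3.1.2 requires permanent discontinuation.
3. The general Grade 3 rule requires discontinuation outside its listed exceptions.

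The third support is incomplete. The Grade 3 exceptions include short-lived flu-like symptoms or fever (up to 6 hours) and short-lived headache, nausea or emesis (up to 24 hours). Section 3.3.1.4 names fever and chills among the signs of an infusion reaction. For some Grade 3 reactions, then, Table 1's own mandate is what requires the stop, so it should not be undercut.

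**Effect of the proposed change.** With the trigger in Section 3.3.1.5 set to Grade 2 only, its coverage is {2} and that of the mandatory row is {3, 4}. The overlap is empty.

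**The case against.** The strongest reply is that the protocol already answers the question. Section 3.3.1.5 is headed for Grade 2 reactions and adds to Table 1 without claiming to override it. The mandatory row is reprinted directly above the sentence at issue. The discretionary wording is permissive: it does not positively authorise another dose after a severe reaction, and an investigator who removes the patient satisfies both texts. Only someone reading the sentence apart from the table would go wrong.

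Most of this stands, and it is why the risk is rated small. It does not remove the contradiction. The heading describes the reaction that brings a patient into the section, while the sentence then sets its own open-ended trigger for the next reaction.

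Three stronger readings are tempting, and the documents do not support them.
- A reader might count every second-reaction clause, including both printings of Table 1's Grade 2 row, as a conflict. Those clauses concern leaving the study, which Sections 3.6.1 and 3.6.2 keep apart from stopping the drug, and the second printing is a duplicate of one table.
- A reader might infer that every recurrence on the slower rate is Grade 3, because Table 1's Grade 3 description mentions symptoms that recur after improving. The Grade 2 row itself provides for a second reaction that is only Grade 2, so the table does not treat recurrence as automatically Grade 3.
- A reader might infer that the trial's results are at risk. The sentence governs dosing of an individual patient. It does not enter the response definitions in Section 6.3, the stage boundaries in Section 10.2 or the analysis population in Section 10.3, which keeps anyone who has received a dose.

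**Conclusion.** The point holds for one sentence, the last in Section 3.3.1.5. For a second IRR of Grade 3 or 4 on the slower rate, it makes optional what Table 1 makes compulsory, and precedence is not stated. The intended meaning is very probably that the mandate prevails.

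The number of patients affected should be very small. Section 3.3.1.1 describes infusion reactions as infrequent and mostly mild to moderate, and only a second, severe reaction on a slowed infusion meets the conflict. That is a qualitative judgement, since the documents give no rate from which to estimate a count. The objective response rate, the Simon two-stage designs and adverse event capture are unaffected.

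The conclusion assumes that Table 1's reference to leaving the study means what it says. If the authors used it loosely to mean leaving treatment, the same contradiction would arise in that row. The correction is still worth making because the defect sits in an operative safety rule and is removed by a small edit.

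**What to change.** In the last sentence of Section 3.3.1.5, change the second-reaction trigger from Grade ≥ 2 to Grade 2, and add: *any Grade 3 or 4 IRR, first or later, requires permanent discontinuation of M7824 per Table 1*.

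Making the same trigger change in the Grade 2 row of Table 1, in both printings, is optional and for consistency only.

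The cost is one edited sentence and one added clause at the next amendment. Procedures, sample size and data collection do not change.
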